12	DATA HANDLING AND RECORD KEEPING	20
12.1	CONFIDENTIALITY	20
12.2	SOURCE DOCUMENTS	20
12.3	CASE REPORT FORMS	20
12.4	DATA MANAGEMENT	20
12.5	DATA PROCESSING.....	21
12.6	DATA SECURITY AND CONFIDENTIALITY	21
12.7	DATA QUALITY ASSURANCE	21
12.8	DATA CLARIFICATION PROCESS	21
12.9	RECORDS RETENTION.....	21
13	STUDY MONITORING, AUDITING, AND INSPECTING	22
13.1	STUDY MONITORING PLAN.....	22
13.2	AUDITING AND INSPECTING	22
14	ETHICAL CONSIDERATIONS.....	22
15	STUDY FINANCES.....	22
15.1	FUNDING SOURCE	22
15.2	CONFLICT OF INTEREST.....	23
15.3	SUBJECT STIPENDS OR PAYMENTS	23
16	PUBLICATION PLAN	23
17	REFERENCES.....	23
18	LIST OF IN-TEXT TABLES.....	25
18.1	SCHEDULE OF EVENTS	25
18.2	INTRAOPERATIVE DATA.....	25
18.3	MONITORING DATA	26
19	LIST OF IN-TEXT FIGURES.....	28
19.1	TETRAGRAPH.....	28

1 Protocol Approval Form

Protocol Number: 19-011705

Study Name: Comparison of Flexor Hallucis Brevis and Adductor Pollicis Muscles (Thumb vs Great Toe) as Sites for Neuromuscular Monitoring with Electromyography after Sugammadex Antagonism

This protocol has been reviewed and approved by the following:

J. [name]
Principal Investigator

01/15/2021

Date

2 List of Abbreviations

AE	Adverse Event/Adverse Experience
AMG	Acceleromyography
CE	Conformite Europeene
CFR	Code of Federal Regulations
cMAPs	Compound Muscle Action Potentials
CRF	Case Report Form
CTSA	Center for Translational Science Activities
DSMB	Data and Safety Monitoring Board
EHR	Electronic Health Record
EMG	Electromyography
FDA	Food and Drug Administration
GCP	Good Clinical Practice
HIPAA	Health Insurance Portability and Accountability Act
IB	Investigator's Brochure
ICU	Intensive Care Unit
IRB	Institutional Review Board
KMG	Kinemography
MMG	Mechanomyography
NMBA	Neuromuscular Blocking Agent
Non-UPIRTSO	Non-Unanticipated Problems Involving Risk to Subjects or Others
PACU	Post Anesthesia Care Unit
PHI	Protected Health Information
PI	Principal Investigator
SAE	Serious Adverse Event/Serious Adverse Experience
SGX	Sugammadex
SOP	Standard Operating Procedure
TOF	Train-of-four
TOFC	Train-of-four count
TOFR	Train-of-four ratio
UPIRTSO	Unanticipated Problems Involving Risk to Subjects or Others
VNRS	Verbal Numeric Rating Scale

3 Study Summary

Title	Comparison of Flexor Hallucis Brevis and Adductor Pollicis Muscles (Thumb vs Great Toe) as Sites for Neuromuscular Monitoring with Electromyography after Sugammadex Antagonism
Running Title	Thumb vs Great Toe Recovery
Phase	N/A
Methodology	Randomized, Open-Label
Overall Study Duration	12 months
Subject Participation Duration	2 to 5 hours
Single or Multi-Site	Single site
Objectives	The primary aim of this study is to assess the onset of neuromuscular blockade and recovery profiles of aminosteroidal NMBAs after sugammadex at the flexor hallucis brevis and adductor pollicis muscles
Number of Subjects	130
Diagnosis and Main Inclusion Criteria	Patients undergoing elective surgery and requiring administration of aminosteroidal NMBAs (rocuronium, vecuronium) intraoperatively
Study Device	TetraGraph
Duration of Administration	Single stimulation of flexor hallucis brevis and adductor pollicis muscles repeated at specific intervals as outlined in the Study Procedures (Section 9.2)

4 Introduction

This document is a protocol for a human research study. This study will be carried out in accordance with the applicable United States government regulations and Mayo Clinic research policies and procedures.

4.1 Abstract

Residual neuromuscular blockade is a common occurrence in the post-anesthesia care unit (PACU) when neuromuscular blocking agents (NMBAs) have been used in the operating room. The only method of reliably detecting residual neuromuscular blockade is through the use of quantitative neuromuscular monitors. Unfortunately, several barriers exist that have prevented the widespread use of these devices. For instance, there is a paucity of quantitative neuromuscular monitors commercially available. Also, two modalities of quantitative monitoring, kinemyography and acceleromyography, rely on movement of the muscles of interest, a characteristic frequently compromised during patient positioning for surgical procedures in which the patient's arms are secured under surgical drapes (laparoscopic, bariatric, robotic, spine, and neurosurgical procedures) or in uncooperative awake patients in the PACU or intensive care unit (ICU). The aim of this investigation is to determine the different muscle sensitivities to NMBA and reversal agents by comparing responses at two different monitoring sites as measured with a new quantitative monitor. The TetraGraph (Senzime AB, Uppsala, Sweden) is a standalone electromyography (EMG)-based quantitative monitor that recently received Conformité Européene (CE) and US Food and Drug Administration (FDA) approvals. EMG measures electrical activity within the muscle following peripheral nerve stimulation, and is unaffected by involuntary patient motion or by restricted muscle movements from surgical positioning. We plan to compare measurements obtained with two Tetraphraph devices, one monitoring the adductor pollicis (thumb) muscle and the other monitoring the flexor hallucis brevis (great toe) muscle, during onset, maintenance, and recovery of neuromuscular blockade. This will include monitoring every 20 sec for onset of blockade (defined as Train-of-four count, TOFC =0) following rocuronium administration, during maintenance of neuromuscular block as required by surgical conditions, and following reversal administration until adequate recovery is documented (train-of-four ratio, TOFR > 0.9).

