4.2 Background

Postoperative residual weakness from neuromuscular blockade continues to be a common problem in the post-anesthesia care unit (PACU). Despite the routine use of reversal agents, a significant number of patients continue to arrive in the PACU with objective evidence of residual neuromuscular blockade (Naguib, Kopman, and Ensor 2007; Cammu et al. 2006; Fortier et al. 2015; Renew and Brull 2019). While not every patient with residual weakness develops a postoperative complication, many can develop avoidable critical respiratory events (Murphy et al. 2008; Berg et al. 1997). Furthermore, special populations such as the elderly, are at particular

risk for developing complications related to postoperative residual weakness (Murphy et al. 2015). The use of quantitative monitoring has been demonstrated to reliably reduce the incidence of postoperative residual weakness and the ensuing complications (Todd, Hindman, and King 2014; Todd and Hindman 2015; Murphy et al. 2011). With an abundance of literature supporting the use of objective neuromuscular monitors, a panel of experts recently recommended the universal adoption of such devices whenever NMBA are utilized (Naguib et al. 2018).

Quantitative neuromuscular monitoring devices objectively measure muscle responses and display the results numerically. This is traditionally accomplished by performing a train-of-four (TOF) stimulation at the ulnar nerve and measuring the response of the adductor pollicis muscle. The degree of muscle weakness is determined by calculating the TOF ratio, which consists of the ratio of the fourth muscle contraction to the first (T4/T1). Adequate recovery that excludes clinically significant weakness from neuromuscular blockade is defined as a TOF ratio ≥ 0.9 , a measurement that can be determined reliably only with a quantitative monitor (Sundman et al. 2000; Eriksson et al. 1997). Although evidence strongly suggests objective monitors should be used perioperatively whenever NMBAs are administered, these devices can be expensive and require additional training. Many clinicians default to using the antiquated qualitative (subjective) neuromuscular stimulating units such as a peripheral nerve stimulator (PNS) (Grayling and Sweeney 2007; Naguib et al. 2010). The major limitation of PNSs is that they cannot measure the muscle responses (TOFR), and therefore cannot assure complete recovery of muscle strength prior to tracheal extubation and spontaneous respiration.

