8.1 Description

TetraGraph device is a FDA approved neuromuscular transmission monitor capable of measuring the depth of neuromuscular block in anesthetized patients who received neuromuscular blocking agents. TetraGraph uses EMG to measure the muscle action potentials that are generated in response to electrical neurostimulation via skin (ECG) electrodes. TetraGraph data is recorded on the monitor's built-in SD card, and all intraoperative data will be recorded and later downloaded for purposes of analysis. The recorded data do not contain PHI, only the date/time of recording, and any additional intraoperative interventions, such as the time of NMBA dose administration, time of antidote administration, time of extubation, etc. These events are flagged in the monitor's integrated SD card recordings.

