8.2 Method for Assigning Subjects to Treatment Groups

This is an open-label pilot investigation and all study participants are assigned to both standard of care and investigational device use in the operating room. The randomization involves the use of dominant vs non-dominant arm. The placement of the lead on the great toe will correspond with the randomization assignment (if patient's dominant hand is right, and then the right great toe will be used).

The randomization will be performed utilizing REDCap and assigned anesthesia clinical care team will be informed of patients' assigned to guide them with the selection of the assigned treatment option.

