9.2 Visit 2 (Randomization and Treatment – day of surgery)

- Elective surgical procedure as per standard of care
- Anesthetic management will include rocuronium, sevoflurane, and sugammadex at the discretion of the attending anesthesiologist as per standard of care practice.
- Prior to induction of anesthesia, Tetragraph electrodes will be placed over the ulnar nerve and the thumb to measure the response of adductor pollicis, and over the posterior tibial nerve and the great toe to measure the response of the flexor hallucis brevis.
- Following induction of anesthesia but prior to NMBA administration, baseline values will be recorded at both muscle groups after instrument calibration.
- Near the conclusion of the operation but prior to reversal of NMBA, another set of measurements will be taken at both muscle groups.
- Intraoperatively, measurements will be taken every minute until the sugammadex administration, as per usual clinical routine.
- After sugammadex administration, measurements will be taken every 20 seconds until the patient's trachea is extubated.
- Anesthesia providers will be guided on the intraoperative management of neuromuscular block based on the responses recorded from the adductor pollicis muscle, as per usual clinical routine.
- Each neurostimulation with the TetraGraph will be conducted simultaneously by a single study team member.
- Following measurements obtained with both devices at these specified time intervals and assuming TOF ratio is >0.9 , the devices will be disconnected and the patient will proceed along the standard recovery pathway.

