18.3 Monitoring data

Study ID				
Date of Surgery (dd / mm / yyyy):				
Initials:		Dominant side:	L / R	Age (yrs):
Wrist circumference (right):		Wrist circumference (left):		
Ankle circumference (right):		Ankle circumference (left):		
Weight (kg):		Height (cm):		BMI:

TetraGraph (TG)

Arm tested: dominant / non-dominant

	Thumb	Toe	TOFR #3 (if needed)
Calibrated baseline TOFR and supramax current			
Time to TOFC=0			
pre-SGX			
+20 sec			
+40 sec			
+60 sec			
+120 sec			
+140 sec			
+180 sec			
+200 sec			
+220 sec			
+240 sec			

+260 sec			
TOFC or TOFR +280 sec			
TOFC or TOFR +300 sec			
TOFC or TOFR at extubation			
Time to recovery following SGX (TOFR ≥ 0.9) (two consecutive measurements)			

19 List of In-Text Figures

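### Which TetraGraph unit goes on which muscle is neither assigned nor recorded, so an uncancelled difference between units could bias the thumb-toe comparison unchecked

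*Combined protocol and SAP*

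**What the plan says.** Section 4.1 describes "two Tetraphraph devices, one monitoring the adductor pollicis (thumb) muscle and the other monitoring the flexor hallucis brevis (great toe) muscle", so every thumb-toe difference is a reading from one instrument minus a reading from another.

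Section 8.2 states what is randomised: "The randomization involves the use of dominant vs non-dominant arm". The toe follows the arm: "The placement of the lead on the great toe will correspond with the randomization assignment". Both units therefore sit on the same side of the body, and the allocation does not touch which unit serves which muscle.

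The form in 18.3 has Thumb and Toe columns, limb circumferences, a calibrated baseline and the supramaximal current. Its entry on allocation is "Arm tested: dominant / non-dominant". It has no field for a unit or serial number.

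Section 9.2 provides that "baseline values will be recorded at both muscle groups after instrument calibration". Section 8.1 says each monitor stores to a built-in SD card and that "all intraoperative data will be recorded and later downloaded for purposes of analysis". Section 10.2 compares the two sites with the Wilcoxon signed rank test and with bias and limits of agreement. It has no term for the unit.

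**The concern.** Within a patient, unit and muscle are completely confounded. What happens across patients depends on placement habits that the plan leaves open. If one monitor tends to travel with the hand set-up and another with the foot set-up, a consistent difference between them enters the mean thumb-toe difference and moves both limits of agreement by the same amount. A larger sample does not shrink that shift. It makes a spurious difference easier to declare significant.

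The planning difference in 10.1 is 0.5 min and the reading interval is 20 s, so a unit that crosses a threshold one reading late on a regular basis would use up two thirds of the target. The exposed endpoint is mainly onset, which is defined by a count of zero (4.1) and so depends on when a unit stops detecting a response. Stimulus delivery is another possible source.

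Because the form does not record the unit, nobody could check from it afterwards whether placement had been balanced.

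**Working it through.** **Inputs.** From 10.1: paired t test, 97 patients, 90% power, difference 0.5 min, significance level 0.05, SD 1.5 min, 130 to be enrolled. From 4.1 and 9.2: readings every 20 s (0.333 min). The documents give no between-unit difference, so b is an assumed range of 3 to 20 s.

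**The plan's own figure.** Two-sided paired t test with noncentral t, SD of differences 1.5 min: noncentrality = 0.5/1.5 × √97 = 3.28, power 90.1%. With 96 patients it is 89.8%. The stated 97 is reproduced. This takes 1.5 min as the SD of the differences. If 1.5 min is the SD at each site, as 10.1 words it, the SD of differences is 1.5 × √(2(1 − ρ)), which equals 1.5 only at a correlation ρ of 0.5.

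**Net bias.** A share p of patients contribute +b and a share 1 − p contribute −b. The mean shift is pb − (1 − p)b = (2p − 1)b.

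**Fixed placement (p = 1), n = 97.** The noncentrality is b/1.5 × √97 with no true difference, and (0.5 − b)/1.5 × √97 when the offset opposes a true 0.5 min difference.

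| Assumed b | False-positive rate | Power for 0.5 min, opposing offset |
|---|---|---|
| 3 s (0.05 min) | 6.2% | 83.3% |
| 5 s (0.083 min) | 8.4% | 77.3% |
| 10 s (0.167 min) | 19.2% | 58.2% |
| 20 s (0.333 min) | 58.2% | 19.2% |

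At 20 s with all 130 patients, the false-positive rate is about 71%.

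**Partly mixed placement, b = 20 s, n = 97.**

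| p | Net bias (2p − 1)b | False-positive rate |
|---|---|---|
| 0.5 | 0 | 5.0% |
| 0.6 | 0.067 min | 7.2% |
| 0.75 | 0.167 min | 19.2% |
| 0.9 | 0.267 min | 41.0% |
| 1.0 | 0.333 min | 58.2% |

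**With units randomised to muscle.** The offset no longer shifts the mean and only adds spread: SD of differences = √(1.5² + b²). At b = 20 s this is √(2.25 + 0.111) = 1.537 min. Power at n = 97 is then 88.7%, and 102 patients restore 90%. Limits of agreement not adjusted for unit widen from ±3.00 to ±3.07 min around the bias. In simulation with random assignment, the false-positive rate stayed at 4.9% to 5.0% for b from 0.1 to 0.5 min.

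**Precision of a check by unit.** With two units split evenly, b is estimated by half the difference between the two assignment groups. Its standard error is 0.5 × 1.5 × √(2/48.5) = 0.152 min, so the 95% interval is about ±0.30 min (18 s).

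**The case against.** The strongest reply is that nothing shows the units differ. They are the same FDA-approved model, and the protocol calls the study a pilot. Several safeguards already exist. Section 4.2 defines the train-of-four ratio as fourth response over first, both from one unit, so a constant gain difference cancels. Each site is calibrated in each patient. A clock offset cancels when dose and response are timed on the same unit, and one team member runs both stimulations together. This stands, and it narrows the concern to differences in detection threshold or stimulus delivery.

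A reader might infer that any difference between units is inseparable from the muscle effect. The documents do not support that. They do not say the study has only two units, or that a unit stays on one muscle. With mixed placement the bias shrinks by the factor 2p − 1.

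A reader might also infer from "The recorded data do not contain PHI, only the date/time of recording" that the recordings cannot be told apart afterwards. That sentence concerns protected health information and is not a full list of what is stored. Separate cards may allow the unit to be recovered, although no procedure links a card to a muscle. Nor is there ground to suppose that thumb and toe values would be confused, since 18.3 has a column for each.

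Finally, the percentages rest on an assumed offset and on a t test, whereas 10.2 plans a Wilcoxon test. That is fair. They show sensitivity and do not predict what will happen.

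**Conclusion.** The gap is real: unit-to-muscle placement is neither assigned nor recorded, and the analysis cannot account for it. It is an uncontrolled risk that is cheap to remove, and not a demonstrated bias or an error in the plan's arithmetic.

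Its size is unknown because the documents give no b. Under the stated assumptions it ranges from negligible (5% false positives when units are balanced, about 6% for a fixed 3 s offset) to serious (58% for a fixed offset of one reading interval). All these rates take the SD of differences as 1.5 min. A larger SD would lower them for the same offset. They apply only to the part of a unit difference that survives calibration and the ratio.

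**What to change.** - **Section 8.2:** have REDCap also randomise, or alternate, which unit goes on the thumb and which on the toe, independently of body side.
- **Table 18.3:** add a unit number for the thumb and one for the toe, and label the monitors to match.
- **Section 10.2:** report the thumb-toe difference by unit assignment as a check. If more than two units are used, adjust for unit instead.

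The protection comes from the balancing. The check by unit is imprecise (about ±18 s at n = 97), so a null result there should not be read as proof that the units agree.

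The cost is one allocation field, one form entry per site and labels, with no added devices, readings or patients. Staff must read the unit assignment before attaching the electrodes. The loss of power is small: 88.7% at n = 97 for a 20 s offset, and the 102 patients that restore 90% are well within the planned 130.

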4.2 Background

Postoperative residual weakness from neuromuscular blockade continues to be a common problem in the post-anesthesia care unit (PACU). Despite the routine use of reversal agents, a significant number of patients continue to arrive in the PACU with objective evidence of residual neuromuscular blockade (Naguib, Kopman, and Ensor 2007; Cammu et al. 2006; Fortier et al. 2015; Renew and Brull 2019). While not every patient with residual weakness develops a postoperative complication, many can develop avoidable critical respiratory events (Murphy et al. 2008; Berg et al. 1997). Furthermore, special populations such as the elderly, are at particular

risk for developing complications related to postoperative residual weakness (Murphy et al. 2015). The use of quantitative monitoring has been demonstrated to reliably reduce the incidence of postoperative residual weakness and the ensuing complications (Todd, Hindman, and King 2014; Todd and Hindman 2015; Murphy et al. 2011). With an abundance of literature supporting the use of objective neuromuscular monitors, a panel of experts recently recommended the universal adoption of such devices whenever NMBA are utilized (Naguib et al. 2018).

Quantitative neuromuscular monitoring devices objectively measure muscle responses and display the results numerically. This is traditionally accomplished by performing a train-of-four (TOF) stimulation at the ulnar nerve and measuring the response of the adductor pollicis muscle. The degree of muscle weakness is determined by calculating the TOF ratio, which consists of the ratio of the fourth muscle contraction to the first (T4/T1). Adequate recovery that excludes clinically significant weakness from neuromuscular blockade is defined as a TOF ratio ≥ 0.9 , a measurement that can be determined reliably only with a quantitative monitor (Sundman et al. 2000; Eriksson et al. 1997). Although evidence strongly suggests objective monitors should be used perioperatively whenever NMBAs are administered, these devices can be expensive and require additional training. Many clinicians default to using the antiquated qualitative (subjective) neuromuscular stimulating units such as a peripheral nerve stimulator (PNS) (Grayling and Sweeney 2007; Naguib et al. 2010). The major limitation of PNSs is that they cannot measure the muscle responses (TOFR), and therefore cannot assure complete recovery of muscle strength prior to tracheal extubation and spontaneous respiration.

There are several types of quantitative neuromuscular monitors. These devices can be incorporated into the anesthesia workstation, allowing data to be seamlessly integrated into the electronic medical record. Unfortunately, this setup can preclude using these monitors in the busy OR environment or PACU, as portability is sacrificed. In contrast, other monitors exist as standalone, portable (hand-held) units.

Aside from portability, objective monitors can further be categorized based on the modality utilized to measure responses. Mechanomyography (MMG) measures the force of contraction of the adductor pollicis (thumb) muscle following ulnar nerve stimulation and has served as the traditional “gold-standard.” MMG responses are precise and reproducible, however the setup is cumbersome and the lack of commercially available devices has relegated MMG to strictly research purposes. Acceleromyography (AMG) measures acceleration of a muscle group (typically the thumb) in response to stimulation (typically the ulnar nerve). This technique is similar to MMG, but instead of measuring the force of muscle contraction, an accelerometer fixed to the thumb measures the acceleration of the thumb in response to ulnar nerve stimulation. Based on Newton’s Second law that states force is proportional to acceleration, the measured acceleration is correlated with the force of contraction in the clinical setting. There are currently two standalone AMG-based monitors available for clinical use: the STIMPOD (Xavant Technologies, Pretoria, South Africa) and the ToFscan (Draeger Medical Inc., Telford, PA).

These devices represent improvements in AMG technology over its predecessor, the TOF-Watch (Schering-Plough Corp., Kenilworth, NJ, USA), as they utilize three-dimensional transducers that can better quantify the complex motion of the thumb. Despite these advances, the use of AMG can be limited due to patient positioning that precludes free motion of the thumb, as well instances of awakening (and uncooperative) patients who may involuntarily move their thumb during measurements, making interpretation of responses impossible. Kinemyography (KMG) is based on similar principles to AMG, and also relies on the thumb being able to move freely. Upon neurostimulation, KMG utilizes a piezoelectric motion sensor that is bent between the thumb and index fingers following muscle contraction. The degree of this bending is quantified and used to determine a TOF ratio. While Datex-Ohmeda (Helsinki, Finland) manufactures a KMG device that can be incorporated into the anesthesia work station, there are no currently available standalone KMG devices. Electromyography (EMG) devices measure electrical activity, termed compound muscle action potentials (cMAPs) following nerve stimulation (typically at the adductor pollicis muscle after ulnar nerve stimulation). As EMG measures cMAPs and does not require freely moving thumbs for accurate measurements, many experts have referred to this monitoring modality as the “new gold standard.”(Naguib et al. 2018) TetraGraph (Senzime AB, Uppsala, Sweden) is a standalone EMG-based device that recently received *Conformité Européene* (CE) and US Food and Drug Administration (FDA) approvals. We have previously investigated this device and presented our findings at several annual meetings such as International Anesthesia Research Society (May 2018, May 2017, May 2013), the Society for Technology in Anesthesia (January 2018), and the American Society of Anesthesiologists (Octotober 2017, October 2012), European Society of Anaesthesiology (June 2018, June 2015). Furthermore, we have submitted abstracts to the PostGraduate Assembly in Anesthesiology in December 2018 as well as a manuscript describing a multi-center, volunteer study investigating TetraGraph versus AMG-based monitors. Our work thus far has found this device to be easy to apply, reliable, and able to provide comparable measurements to other quantitative monitors.

Utilizing recommendations from the Good Clinical Research Practice (GCRP) Guidelines for monitoring of neuromuscular function (Fuchs-Buder et al. 2007), we will investigate the performance of the TetraGraph at two muscle groups: adductor pollicis and flexor hallucis brevis. Specifically, the time points of interest will include the onset of blockade (Train-of-four count =0), maintenance of neuromuscular block as clinically indicated by surgical needs, and recovery from rocuronium blockade with sugammadex, and every 20 seconds following reversal administration until tracheal extubation (as determined by the SOC practice).

